6.5 Stratification and Pooling

For stratified analyses, the randomization stratification factors (IMDC prognostic score and TKI choice) entered into the IRT system at the time of randomization will be used, as follows:

- IMDC prognostic score as entered in IRT (0 [favorable risk] vs 1-2 [intermediate risk] vs 3-6 [poor risk])
- TKI choice as entered in IRT (sunitinib vs cabozantinib)

The IMDC prognostic score will also be derived based on data entered in EDC. When deriving IMDC prognostic score, the latest assessment prior to or on the date of randomization will be used (if not available, then the latest assessment before the date and time of first dose of study drug will be used); if the site used local laboratory data for randomization, the local laboratory data collected in EDC cancer history form will be used. Discrepancies between IMDC prognostic score derived vs IMDC prognostic score as entered in IRT system will be summarized.

If the discrepancy between the IMDC prognostic score (0 vs 1-2 vs 3-6) derived versus as entered in IRT is $\geq 10\%$, a sensitivity stratified analyses using strata based upon derived IMDC

prognostic score per EDC and TKI choice will be performed for the primary and key secondary endpoints.

To avoid unstable estimates, if any stratum (defined by the stratification factors for analysis) have fewer than 6 patients (1% of the estimated total number of patients) or there are no events, that stratum will be pooled with the smallest adjacent stratum for analyses. The smallest adjacent stratum is defined as the stratum with the fewest number of patients or events if the former is a tie, and the adjacent stratum is defined as the stratum with one of the two factors at the same level.

6.6 Definitions

- **Baseline:** In general, baseline will be defined as the last assessment result on or before the randomization date (and time if available).

For safety assessment data (laboratory, vital sign): for treated patients, baseline will be defined as the last assessment result on or before the date (and time if available) of the first dose of study treatment; for patients who are randomized but not treated, baseline will be defined as the last assessment result on or before the randomization date.

If there are multiple valid safety assessments on or prior to the first dose of study treatment:

- For laboratory tests, the latest non missing lab value on or before the first dose date (and time if collected) will be used as the baseline in the analyses. If multiple observations exist on the latest collection date (and time if collected), then the first observation is used as baseline.
- For ADA, the record related to the most recent assessment among those records where date (and time if collected) of the ADA assessment being performed for a specific drug is on or before to the date (and time if collected) of the first dose date of that specific drug.

Pre-treatment AEs will be defined as AEs with an onset date prior to, but not including, the day of the first dose of study treatment.

- **Study Day:** There is no study day zero. In general, Study Day 1 is the date of randomization.
 - For post-randomization days, study day is calculated as:
assessment date – randomization date + 1
 - For pre-randomization days, study day is calculated as:
assessment date – randomization date

For safety analysis, study day is calculated and presented based on the first dose date as defined below.

- **First Dose Date:** First dose date will be defined as the date of first dose of study treatment, Cycle 1 Day 1 (C1D1). Note, per protocol, the first dose date may be ≤ 5 days after the date of randomization. If the randomization date and the first dose date is not on the same day, then the date of randomization will be different from C1D1. Safety data will be calculated and presented based on First Dose Date.

- **Treatment-emergent/Extended Treatment-emergent Period:**

For patients on treatment, both the treatment-emergent period and the extended treatment-emergent period will be defined as the period of time on or after the day (and time, if collected and not missing) of the first dose of study treatment.

For patients off treatment, the treatment-emergent period is defined as the period of time on or after the day (and time, if collected and not missing) of the first dose of study treatment, until: the date of (initiation of new anticancer therapy – 1 day) or (30 days after the date of the last dose of any study treatment), whichever is earlier.

The extended treatment-emergent period will be defined as the period of time on or after the day (and time, if collected and not missing) of the first dose of study treatment until earlier date of (initiation of new anticancer therapy – 1 day) and (100 days after the date of the last dose of any study treatment).

- **Treatment-Emergent Adverse Event (TEAE):**

TEAEs are AEs with an onset date (and time, if collected and not missing) within the treatment-emergent period, or extended treatment-emergent period depending on the analysis

Incomplete start and end dates for TEAEs will be imputed. Any AE will be considered as a TEAE if its status cannot be fully determined because of incomplete data.

- **Last Known Alive Date:** Last known alive date will be defined as the latest alive date on or before data cutoff date, captured from multiple sources. Note that if there is an event date (either an assessment or death) beyond the data cutoff date, the last known alive date will be the data cutoff date. If a patient died before or on the data cutoff date, the last known alive date will be set as the death date. The last known alive date will not be imputed, except in the case that the death date is partially missing (see details in Section 6.4)

6.7 Study Drug Exposure

For NKTR-214 and nivolumab in Arm A, the following parameters will be calculated:

- Exposure duration (days) for each drug: Date of last dose – date of first dose (C1D1) + 1

For NKTR-214 in Arm A, the following parameters will be calculated:

- Total number of infusions: Total number of infusions for which the patient received a non-zero dose across all cycles

- Cumulative dose (mg/kg): Total actual dose (mg/kg) the patient received across all cycles, defined as the sum of actual doses (mg/kg) received across all cycles
- Average dose per infusion (mg/kg): Cumulative dose (mg/kg) / Total number of infusions
- Average duration of infusion (min): Total infusion time (min) / Total number of infusions; where total infusion time = summation of (completion time of infusion – start time of infusion) for all infusions of a patient
- Actual dose intensity (mg/kg/week): [Cumulative dose (mg/kg) / (Exposure duration (in days) + 20 days)] × 7
- Expected dose intensity (mg/kg/week) = (0.006 mg/kg) / (3 weeks) = 0.002 mg/kg/week
- Relative dose intensity (%): (Actual dose intensity / Expected dose intensity) × 100

For Nivolumab in Arm A, the following parameters will be calculated:

- Total number of infusions: Total number of infusions for which the patient received a non-zero dose across all cycles
- Cumulative dose (mg): Total actual dose (mg) the patient received across all cycles, defined as the sum of actual doses (mg) received across all cycles
- Average dose per infusion (mg): Cumulative dose (mg) / Total number of infusions
- Average duration of infusion (min): Total infusion time (min) / Total number of infusions; where total infusion time = summation of (completion time of infusion – start time of infusion) for all infusions of a patient
- Actual dose intensity (mg/week): [Cumulative dose (mg) / (Exposure duration (in days) + 20 days)] × 7
- Expected dose intensity (mg/week) = (360 mg) / (3 weeks) = 120 mg/week
- Relative dose intensity (%): (Actual dose intensity / Expected dose intensity) × 100

For Sunitinib in Arm B, the following parameters will be calculated:

- Exposure duration (days): Date of last dose – date of first dose (C1D1) + 1
- Total number of doses: Total number of doses the patient received
- Average daily dose (mg/day): Sum of all sunitinib doses in mg actually received / Exposure of duration (in days)
- Expected daily dose (mg/day): 33.33 mg/day (= 50 mg × 28 days / 42 days)
(Note that sunitinib treatment consists of 50 mg PO daily dose for 4 weeks followed by 2 weeks of a washout period)
- Relative dose intensity (%): (Average daily dose / Expected daily dose) × 100

For Cabozantinib in Arm B, the following parameters will be calculated:

- Exposure duration (days): Date of last dose – date of first dose (C1D1) + 1
- Total number of doses: Total number of doses the patient received
- Average daily dose (mg/day): Sum of all cabozantinib doses in mg actually received / Exposure of duration (in days)
- Expected daily dose (mg/day): 60 mg/day or 40 mg/day (40 mg for patients with mild to moderate hepatic impairment [Child-Pugh score A or B])
- Relative dose intensity (%): $(\text{Average daily dose} / \text{Expected daily dose}) \times 100$

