5.13 Dosage Modification

Every effort should be made to follow planned dosing schedules for all study drugs in both treatment arms. Study drug administration may be delayed or modified for toxicity as described below and must be discontinued as required by criteria described in Section 5.14.

Dose modification for NKTR-214 and nivolumab in Arm A may be considered independently based on Investigator assessment of relationship of a toxicity to each of the study drugs. If only one of the study drugs meets the criteria for dose delay, then administration of the other study drug may be continued or delayed at the discretion of the Investigator. Likewise, in the event that one of the study drugs in Arm A is permanently discontinued due to toxicities, the other can continue to be administered.

Patients who require delay of nivolumab or NKTR-214 should be re-evaluated weekly or more frequently if clinically indicated and should resume treatment with combination of NKTR-214 and nivolumab when retreatment criteria are met (Section 5.13.7). Immuno-oncology agents are associated with AEs that can differ in severity and duration from AEs caused by other therapeutic classes. NKTR-214 and nivolumab are considered an immuno-oncology agent in this protocol. Early recognition and management of AEs associated with immuno-oncology agents may mitigate severe toxicity.

For patients randomized to Arm A: NKTR-214 or nivolumab administration defines a scheduled nominal dosing visit (i.e., Cycle X Day 1, Cycle X Day 22). If a patient is assessed for an intended nominal dosing visit but study drug is not administered (e.g., due to an AE requiring dose delay, drug unavailable), any assessments performed during that visit should be recorded as “unscheduled.” When study drug administration resumes, all assessments should be performed as scheduled for the next nominal dosing visit (i.e., Cycle X Day 1 or Cycle X Day 22 Visit).

For patients randomized to Arm B: Cycle 1 Day 1 is defined by the date that the first dose of sunitinib or cabozantinib is administered. Within a cycle, missed doses of sunitinib should be skipped and not replaced. Scheduled Cycle X Day 1 and Cycle X Day 22 visits are fixed relative to Cycle 1 Day 1, regardless of dose delays. If drug dosing is delayed at the time of these scheduled visits (e.g., due to an AE requiring dose delay, drug unavailable), the cycle visit is not shifted and all assessments should be performed as scheduled.

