5.2.2 Arm B: Treatment of Investigator's Choice

Patients randomized to TKI will receive a widely used standard-of-care agent: sunitinib or cabozantinib. Sunitinib is a vascular endothelial growth factor (VEGF) receptor TKI that is approved and recommended for the treatment of advanced RCC across prognostic groups. The starting dose of sunitinib is 50 mg, and it is administered po once daily for 4 weeks followed by 2 weeks off (6-week cycle). Cabozantinib is a small molecule inhibitor of the tyrosine kinases c-Met, AXL, and VEGFR2, and has been shown to reduce tumor growth, metastasis, and angiogenesis. Cabozantinib has been evaluated in both first-line and second-line settings in advanced RCC. The starting dose of cabozantinib is 60 mg (40 mg for patients with moderate hepatic impairment [Child-Pugh score B]) and it is administered po once daily.

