7.2 Important Protocol Deviations

Important protocol deviations are defined as protocol deviations that fall into the following categories:

- Violated key inclusion/exclusion criteria
 - Patient did not have advanced or metastatic RCC with a clear-cell component
 - Patient received prior systemic therapy
 - Patient had active brain metastases
 - Patient did not meet inclusion/exclusion criteria for lab values (e.g., absolute neutrophil count [ANC], platelet count, hemoglobin, serum creatinine, alanine aminotransferase [ALT], aspartate aminotransferase [AST], total bilirubin, urine protein creatinine ratio [UPCR])
 - Patient had a Karnofsky Performance Status of less than 70%
 - Patient required more than 2 anti-hypertensive medications for managing hypertension
 - Patient received prior palliative radiotherapy within 2 weeks prior to randomization
- Received wrong treatment or significant incorrect dose
 - Treated differently from the randomized assignment
 - Relative dose intensity >125% for study drug (programmatically derived). Received important prohibited medication during study participation
 - Any antineoplastic therapy (i.e., chemotherapy, hormonal therapy, immunotherapy, extensive non-palliative radiation therapy, or investigational agent)
- Missing critical primary/key secondary efficacy assessment
 - The baseline disease assessment is missing in BICR data (programmatically derived)

- Stratification error
- Issues that affect patient rights
 - Patient did not sign the informed consent for the study before randomization (programmatically derived)
 - Patient developed withdraw criteria during the study but were not withdrawn (manual review)
- Other issues that may significantly impact the completeness, accuracy, and/or reliability of key study data or that may significantly affect a patient's rights, safety, or well-being

Final determination of important protocol deviations will be reviewed by the study team (including Clinical Trial Lead (CTL), the Medical Monitor, and the statistician).

The number and percentage of patients in each important protocol deviations category and sub-category will be summarized by treatment arm for the ITT I/P-risk population and ITT all-risk population. All protocol deviations will be listed.

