7.4.4 Study Drug Exposure

Overall exposure to each study drug will be summarized for the Safety I/P-risk population and the Safety all-risk population. Overall exposure to each study drug will be summarized in terms of exposure duration, number of infusions/doses, and relative dose intensity. The following summaries will also be performed:

- Time from randomization to first dose of study therapy (0 to 5 days, > 5 to 7, > 7 to 14, > 14 to 21, > 21 to 28, > 28)
- Relative dose intensity (%) using the following categories: < 50%; 50 - < 70%; 70 - < 90%; 90 - < 110%; \geq 110%
- For Arm A, the number of patients with at least one dose infusion interruption, the reason for interruption, and the number of infusion interruptions per patient
- For Arm A, the number of patients with at least one dose delay (either study drug) or dose reduction (for NKTR-214 only) and their reason(s)
- For Arm B, the number of patients with dose reduction and dose missed will be tabulated along with their reason(s)
- For NKTR-214, the time to first dose reduction and time to first dose infusion interruption will be summarized using descriptive statistics (mean, median, minimum, maximum)

All study exposure data will be presented in a data listing.

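### SAP 6.7 overstates sunitinib relative dose intensity (150% for full dosing that ends in Cycle 1), and its cabozantinib reference for Child-Pugh A conflicts with SAP 5.2.2 and Protocol 5.4.1; both feed the >125% deviation flag

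*SAP*

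**What the plan says.** For sunitinib, SAP 6.7 sets exposure duration as last dose date minus first dose date plus 1. It takes the average daily dose as "Sum of all sunitinib doses in mg actually received / Exposure of duration (in days"). The reference is "Expected daily dose (mg/day): 33.33 mg/day", derived as 50 mg × 28 / 42. Relative dose intensity (RDI) is the first over the second, as a percentage.

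For both Arm A drugs, the same section adds 20 days to the exposure duration before dividing.

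For cabozantinib, SAP 6.7 gives a reference of 60 mg/day, or 40 mg/day: "40 mg for patients with mild to moderate hepatic impairment", which it spells out as Child-Pugh A or B. SAP 5.2.2 gives the starting dose as 60 mg, with "40 mg for patients with moderate hepatic impairment [Child-Pugh score B"]. Protocol 5.4.1 also attaches 40 mg to Class B and states that Class A needs no reduced starting dose.

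RDI is used in two places. SAP 7.2 lists as an important deviation "Relative dose intensity >125% for study drug (programmatically derived"), under the heading for wrong treatment or a significantly incorrect dose, and adds that "Final determination of important protocol deviations will be reviewed by the study team". SAP 7.4.4 tabulates "Relative dose intensity (%) using the following categories": <50%, 50 to <70%, 70 to <90%, 90 to <110%, and ≥110%.

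**The concern.** The two sides of the sunitinib ratio cover different windows. The numerator stops at the last tablet, so the final two-week rest never enters it. The denominator is an average that includes that rest. RDI is therefore above 100% for every on-schedule patient whose last dose falls in an on-period, and the excess is largest for those who stop earliest. No comparable term corrects for it, although Arm A has one.

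For cabozantinib there are no rest weeks and no window problem. The issue is that the reference dose for Class A patients disagrees with the starting dose given elsewhere. Class A patients are eligible, since Protocol 4.1 excludes only Class C.

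At stake is the credibility of the Arm B exposure and deviation tables. Sunitinib patients who took exactly what was scheduled can be reported as significantly misdosed, and the RDI bands can present an under-dosed comparator patient as fully dosed.

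**Working it through.** **Inputs.** Sunitinib 50 mg daily, 28 days on and 14 off (Protocol 5.4.1.3); formulas from SAP 6.7; flag above 125% from SAP 7.2; bands from SAP 7.4.4.

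**The plan's own figure.** 50 × 28 / 42 = 33.33 mg/day. This reproduces; the number is right and the mismatch lies in the windows.

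**Sunitinib, uninterrupted 50 mg.** Let L be the day of the last dose (first dose = day 1) and n the number of scheduled on-days up to L. Then RDI = 100 × (50n / L) / 33.33.

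| L | n | mg/day | RDI |
|---|---|---|---|
| 1 to 28 | L | 50.00 | 150% |
| 43 | 29 | 33.72 | 101.2% |
| 53 | 39 | 36.79 | 110.4% |
| 70 | 56 | 40.00 | 120.0% |
| 105 | 77 | 36.67 | 110.0% |
| 112 | 84 | 37.50 | 112.5% |
| 154 | 112 | 36.36 | 109.1% |
| 364 | 252 | 34.62 | 103.9% |

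After Cycle 1 the maximum is 120% (day 70), so under on-schedule dosing only Cycle 1 stops exceed 125%. Last doses on days 1–28, 53–70 and 105–112 fall in the ≥110% band; from Cycle 4 onward the peak is 109.1%, which stays in the 90 to <110% band.

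**Sunitinib with missed or reduced doses.** The protocol says "Within a cycle, missed doses of sunitinib should be skipped and not replaced", so the schedule does not stretch to make up for them.

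| Pattern | RDI by SAP 6.7 | Received / scheduled to last dose |
|---|---|---|
| 24 of 28 doses, L = 28 | 24×50/28 = 42.86 mg/day → 128.6%, flagged | 24/28 = 85.7% |
| 23 of 28 doses, L = 28 | 41.07 mg/day → 123.2%, not flagged | 23/28 = 82.1% |
| 19 of 28 doses, L = 28 | 33.93 mg/day → 101.8% | 19/28 = 67.9% |
| 50 mg in Cycle 1, 37.5 mg in Cycle 2, L = 70 | (1400 + 1050)/70 = 35 mg/day → 105% | 2450/2800 = 87.5% |

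The third row moves from the 50 to <70% band to the 90 to <110% band. The fourth moves from 70 to <90% to 90 to <110%.

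**Arm A comparison.** For k infusions 21 days apart, exposure is 21(k − 1) + 1 days. Adding 20 gives 21k days, so RDI is exactly 100%.

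**Cabozantinib, Class A, 40 mg/day reference.** 60/40 = 150%; 50/40 = 125%, which is not above the threshold; 40/40 = 100%. The flag therefore trips whenever the average exceeds 50 mg/day. Against a 60 mg/day reference, the 60 and 40 mg averages score 100% and 66.7%.

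**The case against.** The strongest reply is that the consequences are limited and partly caught elsewhere.

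- **Under-dosing is visible in other outputs.** SAP 7.4.4 also tabulates Arm B patients with missed doses and dose reductions, with reasons, and lists all exposure data. This stands: under-dosing is masked in the RDI bands, not in the report as a whole. The bands would still be wrong.
- **The study team reviews deviations.** True, and the team includes the Medical Monitor and the statistician. But no criterion is given for overturning a computed flag, and review does not correct the RDI table.
- **Few bands change.** For on-schedule sunitinib this is right: only the day ranges listed above shift. Patients with missed or reduced doses shift only if the overstatement carries them across a cut-point, and cabozantinib is affected only in Class A.
- **The Arm A correction is not like-for-like.** Also right: 20 days is one dosing interval less a day, and the sunitinib problem comes from its on/off pattern. Arm A shows only that on-schedule dosing is meant to score 100%.
- **Calling the cabozantinib flag false presumes the 60 mg reference.** Accepted. The point is that the passages disagree, not that either is correct.

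**Conclusion.** The concern holds. Following SAP 6.7 as written gives sunitinib RDI values above 100% for on-schedule dosing with a last dose in an on-period: 150% for any stop in the Cycle 1 on-period, up to 120% in Cycle 2, 112.5% in Cycle 3 and 109% in Cycle 4, and about 104% at one year. The 125% flag is tripped by full or near-full dosing that ends in Cycle 1 (24 or more of 28 doses when the last is on day 28). The cabozantinib reference for Class A contradicts two other passages and produces 150% for unreduced 60 mg.

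These figures assume 50 mg on the stated calendar except where a pattern is named. The documents do not say how many patients stop sunitinib in Cycle 1 or are Class A on cabozantinib, so the number affected cannot be given.

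The effect is confined to Arm B descriptive exposure and deviation summaries. SAP 6.3 defines no per-protocol set, so the ORR, OS and PFS analyses and the safety analysis sets do not change. It should be corrected, but it does not threaten the trial's conclusions.

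**What to change.** **Sunitinib.** Define RDI as cumulative dose received divided by cumulative dose scheduled, from first to last dose date on the 4-weeks-on/2-weeks-off calendar, times 100. This returns 100% for any on-schedule stop. Protocol 5.13 already fixes Arm B visits relative to Cycle 1 Day 1 regardless of delays, so the calendar is well defined. A flat +14 days is not a substitute: it works after a completed on-period (1400/42 = 33.33 mg/day, 100%) but scores a fully dosed day-14 stop at 14 × 50 / 28 = 25 mg/day, or 75%. Adding the 14 days only after a completed on-period, and using dose scheduled to date otherwise, is an acceptable alternative.

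**Cabozantinib.** Reconcile the Child-Pugh wording in SAP 6.7 with SAP 5.2.2 and Protocol 5.4.1, and make the RDI denominator follow the reconciled text. Which dose applies is for the sponsor to settle.

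**Cost.** Two SAP edits and the matching programming. No new data and no burden on patients.

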7.0 STATISTICAL ANALYSIS

7.1 Patient Disposition

A summary of patient disposition will display the number of patients who were randomized and the number that comprised each analysis population by treatment arm for the ITT I/P-risk population and ITT all-risk population. In addition, the number of patients who discontinued study drug and the number of patients who exited the study, both overall and by reason, will be presented by treatment arm for the ITT I/P-risk population and the ITT all-risk population. Descriptive statistics for time to NKTR-214 discontinuation (mean, median, min, max) will be summarized for the patients who discontinued NKTR-214.

All disposition data will be presented in a data listing.

